3.2.2 Secondary Endpoints

Immunogenicity

- Humoral immune response as measured by neutralization antibody (NAb) assay at baseline (Day 0) and at 4 weeks after second injection (Week 8).

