3.3 Study Definitions and Derived Variables

The baseline value will be defined as the last value obtained prior to the first injection of study product on Day 0.

Individual neutralization antibody (NAb) assay results will be reported as a titer. The lower limit of detection for the NAb assay is 15 reciprocal serum dilution and the lower limit of confidence is 30 reciprocal serum dilution. Values below the limit of detection will be imputed as 15 if not already imputed prior to analysis. For analysis, the arithmetic mean of repeated results for each sample will be computed and used as the response for all subsequent calculations.

Fold-rise (NAb) is a measure that describes how much the NAb titer changes from an initial to a final value. The fold-rise is calculated as the ratio of the final value to the initial value.

Positive response rate (NAb) will be measured as the proportion of subjects with a positive response, defined as a reciprocal serum dilution ≥ 30 .

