9 IMMUNOGENICITY EVALUATION

Specimens to evaluate immunogenicity will be taken at baseline and at specified time points. The primary immunogenicity timepoint is 4 weeks after the second injection. Measurements of CHIKV-specific humoral immune responses will be assessed by neutralization antibody (NAb) assays. A listing of individual titer levels and the corresponding planned and actual collection dates are presented in **Appendix III, Listing 16.2.6**.

At some sites, positive baseline Week 0 neutralization antibody assay results were reported. ELISA response data, captured as part of the screening eligibility process, have been received by the Sponsor from the laboratory. When raw ELISA data is received, baseline ELISA responses will be assessed in relation to neutralization antibody data and results will be reported. For further information, a separate analysis plan will be created to elaborate on specific analyses to be performed.

The principle immunogenicity endpoint is measured at Week 8 by neutralization assay.

Descriptive analyses will be presented by study day, age group, and treatment group, aggregated over all study sites and by site. If none or a very small number of placebo group subjects have a neutralization response, their results will only be reported for the positive response rate summaries and omitted from other analyses. This approach is taken to achieve brevity and easier understanding of results when the control group has no meaningful responses.

Summaries include:

- GMT and their confidence intervals (**Table 14.2.1, Appendix I**)
- Geometric mean ratio (GMR) of results obtained at baseline (Week 0) to results obtained at Week 8 and its 95% CI. (**Table 14.2.1, Appendix I**)
- Positive response rates, as defined by an assay-specific post dose response, and their exact 95% CI (**Table 14.2.1, Appendix I**)
- Reverse cumulative distribution of the neutralization assay results (**Figure 14.2.1, Appendix II**)
- Boxplots of titer values (**Figure 14.2.2, Appendix II**).

These summaries will be repeated for all exploratory research tests used to measure exploratory immunogenicity endpoints at the timepoints for which there are data.

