Appendix II: Figure Mock- Ups

for

VRC 704

Study Title:

**Phase 2 Randomized, Placebo-Controlled Trial to Evaluate the Safety and Immunogenicity of a
Chikungunya Virus-Like Particle Vaccine,
VRC-CHKVLP059-00-VP, in Healthy Adults**

Version 1.0

Prepared and distributed by:
The Emmes Corporation
Rockville, Maryland

THIS COMMUNICATION IS PRIVILEGED AND CONFIDENTIAL

Table of Contents

FIGURE 14.1.1: CONSORT Flow Diagram By Age Stratum.....	2
FIGURE 14.2.1: Reverse Cumulative Distribution of the Assay by Study Day, Site, and Treatment Group.....	3
FIGURE 14.2.2: Boxplots with Overlaid Scatter Plots Summarizing the Assay by Study Day, Site, and Treatment Group.....	4
FIGURE 14.3.1.1: Maximum Severity per Subject by Days Post Treatment	5
FIGURE 14.3.1.2: Number and Severity of Non-Serious Adverse Events by MedDRA® System Organ Class	6
FIGURE 14.3.1.3: Non-Serious Adverse Events by Severity	7
FIGURE 14.3.1.4: Number and Relationship of Non-Serious Adverse Events by MedDRA® System Organ Class	8
FIGURE 14.3.1.5: Non-Serious Adverse Events by Relationship to Treatment.....	10
FIGURE 14.3.4.1: Laboratory Results by Scheduled Visits: Mean Changes from Baseline by Laboratory Parameter and Treatment Group.....	11
FIGURE 14.4.1-14.4.x: Boxplot of Vital Signs by Scheduled Visits	12
FIGURE 14.5.1-14.5.x: Boxplot of Laboratory Results by Scheduled Visits.....	13
FIGURE 15.1.1: Kaplan-Meier Curves for Time to Occurrence of Clinical CHIKV Infection Post Dose One	14
FIGURE 15.1.2: Kaplan-Meier Curves for Time to Occurrence of Clinical CHIKV Infection Post Dose Two	14
FIGURE 15.1.3: Kaplan-Meier Curves for Time to Occurrence of PCR Confirmed CHIKV Infection Post Dose One	14
FIGURE 15.1.4: Kaplan-Meier Curves for Time to Occurrence of PCR Confirmed CHIKV Infection Post Dose Two.....	14

**FIGURE 14.1.1:
 CONSORT Flow Diagram By Age Stratum**

[Implementation Note: In the SAP, include a blank diagram with the possible reasons why subjects may be excluded from analyses. The reasons for exclusion should be in line with the SAP text.]

[figure not shown]

FIGURE 14.2.1:
Reverse Cumulative Distribution of the [specific assay] by Study Day, Site, and Treatment Group <<Age Stratum>>

Note: These are illustrative curves. The actual curves compare CHIKV vaccine and placebo. For neutralization (the primary immunogenicity endpoint), the time periods to be used are Days 0, 28 and 56.

[figure not shown]

FIGURE 14.2.2:

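### The Week 8 NAb positive response rate ignores the Day 0 titer, so it measures seropositivity rather than response; the GMR is also worded as the reciprocal of fold-rise

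*Combined protocol and SAP*

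**What the plan says.** SAP 3.3 defines the responder measure: "Positive response rate (NAb) will be measured as the proportion of subjects with a positive response, defined as a reciprocal serum dilution" of 30 or more. No baseline condition is attached. SAP 9 lists the summary as "Positive response rates, as defined by an assay-specific post dose response, and their exact 95% CI", and the footnote to Table 14.2.1 leaves the positivity criterion as a placeholder.

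SAP 9 also states: "At some sites, positive baseline Week 0 neutralization antibody assay results were reported". It gives neither a count nor a cut-off. It adds that baseline ELISA responses will be assessed in relation to the NAb data, and that "a separate analysis plan will be created to elaborate on specific analyses to be performed".

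None of the populations in SAP 6.3 depends on baseline NAb status, and SAP 6.4 limits subgroups to age stratum and site. Eligibility (SAP 4.3, inclusion criterion 14) rests on a negative screening antibody assay, not on the Day 0 NAb titer. Table 14.2.1 shows the GMT at baseline and Week 8, the GMR, and the Week 8 positive rate. It has no baseline positive rate and no Week 8 rate by baseline status.

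On change from baseline, SAP 3.3 says "The fold-rise is calculated as the ratio of the final value to the initial value". SAP 9 plans the "Geometric mean ratio (GMR) of results obtained at baseline (Week 0) to results obtained at Week 8".

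**The concern.** The secondary objective is the immune response to the vaccine at Week 8. A rule that looks only at the Week 8 titer cannot separate a response from antibody already present on Day 0. A placebo recipient whose baseline antibody persists is counted as a responder, and so is a vaccinee whose titer was already 30 or more and never rose. The planning text (SAP 5.2) did not anticipate vaccine-specific neutralizing antibody in the non-vaccinated group. SAP 9 records baseline positives but leaves the responder rule as it was.

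The trial is meant to inform later efficacy trials (SAP 6.8). A reader who takes the two Week 8 rates as response rates would see a placebo response that is not one and a gap between arms that is too small. Because the positives arose at some sites only, by-site rates there can be affected more than the overall rate.

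The GMR wording is a separate matter. Read literally, it inverts the fold-rise that SAP 3.3 defines.

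**Working it through.** **Inputs from the documents.** Planned evaluable n = 180 per arm (200 less 10%; SAP 5). Vaccinee log titer at the peak visit: mean 7.41, SD 0.67, with planning SDs of 0.70, 1.0 and 1.5 (SAP 5.2). Cut-off 30 and floor 15 (SAP 3.3).

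**Reproducing the plan's figure.** The 95% CI for the GMT is exp(7.41 ± 1.973 × SD/√180), where 1.973 is the t quantile on 179 degrees of freedom.

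| SD | Recomputed | SAP Table 4 |
|---|---|---|
| 0.70 | 1490.8 to 1831.6 | 1490.7 to 1831.7 |
| 1.0 | 1426.4 to 1914.3 | 1426.6 to 1914.1 |
| 1.5 | 1325.3 to 2060.3 | 1324.8 to 2061.1 |

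The inputs are read correctly.

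**True response v in baseline-negative vaccinees.** P(titer < 30) = Φ((ln 30 − 7.41)/SD), with ln 30 = 3.401.
- SD 0.67: Φ(−5.98), about 1 in 10⁹.
- SD 1.5: Φ(−2.67) = 0.0038, so v = 99.6%.

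Protocol 1.3 agrees: neutralizing antibody was detected in all Phase 1 subjects by 4 weeks after the second vaccination.

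**Effect of the rule.** Let b be the fraction with a Day 0 titer of 30 or more that stays there to Week 8. The documents do not give b, so a range is assumed. Without incident infection:
- placebo rate = b
- vaccine rate = b + (1 − b)v, a shift of b(1 − v)
- apparent contrast = (1 − b)v, where v is wanted

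With v = 99.62%:

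| b | Placebo counted positive, of 180 | Vaccine-rate shift (points) | Apparent contrast (points) |
|---|---|---|---|
| 1% | about 2 | 0.004 | 98.6 |
| 2% | about 4 | 0.008 | 97.6 |
| 5% | 9 | 0.02 | 94.6 |
| 10% | 18 | 0.04 | 89.7 |
| 20% | 36 | 0.08 | 79.7 |

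The contrast wanted is 99.6 points in every row. The upper values of b are illustration only.

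**With the baseline-negative rate (b = 10%, exact 95% CI).** Placebo goes from 18/180 = 10.0% (6.0 to 15.3) to 0/162 = 0% (0 to 2.3). If all vaccinees respond, the lower limit goes from 0.025^(1/180) = 98.0% with 180/180 to 0.025^(1/162) = 97.7% with 162/162. Little precision is lost.

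**GMR direction.** exp(7.41) = 1652. Over the floor of 15, Week 8/Week 0 = 1652/15 = 110. As worded in SAP 9 it is 15/1652 = 0.009, which prints as 0.01 in the two-decimal format of Table 14.2.1.

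**The case against.** The strongest case against has four parts.

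**The sponsor saw the issue.** SAP 9 reports the baseline positives and announces a separate plan in the same paragraph. This stands to the extent that one can say only that the rate is not in this SAP. The separate plan is tied to baseline ELISA against NAb, its content is not available here, and a baseline-negative rate needs no ELISA data.

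**The vaccine rate hardly moves.** This stands in full. A reader might infer that the vaccine response rate is materially inflated, but the documents do not support that: the shift is at most about 0.08 points even at b = 20%. If v were only 95%, a value with no source in the documents, the shift at b = 10% would be 0.10 × 0.05 = 0.5 points, still less than one subject in 180 (0.56 points).

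**The comparison is valid and baseline data are shown.** Randomization within site and age stratum balances baseline positives in expectation, so a reading that Fisher's test is biased would be wrong. The concurrent placebo rate shows background seropositivity, Table 14.2.1 gives the baseline GMT, and the note to Figure 14.2.1 says "For neutralization (the primary immunogenicity endpoint), the time periods to be used are Days 0, 28 and 56". None of these is a response rate that accounts for Day 0. SAP 9 also drops placebo results other than the positive rate when very few placebo subjects respond, so in that case the placebo GMT and GMR would not show that titers stayed flat.

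**Incident infection also contributes.** Subjects live in endemic areas, and SAP 6.3 provides for censoring after PCR-confirmed infection only under the per-protocol population. The placebo rate is therefore b plus any new infections, and a baseline-negative rate removes only the first part.

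On the GMR, the wording is probably a slip, and inference on the reciprocal is identical. But neither the SAP 9 summaries nor Table 14.2.1 mentions fold-rise, so nothing there settles the direction.

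**Conclusion.** The point holds as a minor one about interpretation. As written, the Week 8 positive response rate is a seropositivity rate. The placebo rate rises to about b plus incident infections, the apparent contrast falls from v to about (1 − b)v, and by-site rates can mislead where baseline positives occurred. The vaccine-arm rate is essentially unaffected and the test between arms remains valid.

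The size is uncertain because b is not given. The screening assay probably keeps it small: Table 14.1.1 counts a positive or indeterminate IgG or IgM result as a screening failure. The figures assume that baseline titers of 30 or more persist to Week 8, that 180 per arm are evaluable, and that the peak-visit distribution applies at Week 8. The Phase 1 statement that antibody was detected in all subjects does not name the cut-off of 30. The wording of the rule and the reversed GMR are certain from the text.

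**What to change.** In SAP 3.3, SAP 9 and Table 14.2.1:

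- Add the Week 8 positive response rate (titer 30 or more, exact 95% CI) among subjects with a Day 0 titer below 30, by arm: overall, and separately by site and by age stratum, not crossed.
- Report the number with a Day 0 titer of 30 or more by arm and site, and show their fold-rise descriptively. Set no new responder threshold for them, since Protocol 6.4.5 plans an interim look at Week 8 immunogenicity and SAP 6.6 cites an interim plan dated 19 January 2018.
- Keep the all-subject rate, labelled as Week 8 seropositivity, and cross-reference the separate plan announced in SAP 9.
- State GMR = Week 8 / Week 0, in line with fold-rise in SAP 3.3.

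The cost is SAP wording and a few columns in Table 14.2.1. Day 0 NAb is already measured and the cut-off is the existing one, so no samples, assays or protocol change are needed; Protocol 6.4 already allows further cohorts in the SAP. The downside is a slightly smaller denominator (162 of 180 per arm if b = 10%) and small counts by site.

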4 INVESTIGATIONAL PLAN

4.1 Overall Study Design and Plan

VRC 704 is a Phase 2 multicenter, randomized, placebo-controlled, double-blind parallel group study as summarized in **Table 1** below. It examines the safety and immunogenicity of a 2-injection vaccine regimen (Day 0 and 28) with the CHIKV VLP vaccine or PBS placebo in healthy adults (N=200 per group). Subjects will be randomly assigned in a 1:1 allocation to active vaccine or placebo control using a randomized block design stratified by age within each study site. The expected duration of time on the study per subject is approximately 72 weeks.

Table 1: Study Schema

Group	Number of Subjects	VRC 704 Study Injection Schedule	
		Day 0	Day 28(+14)
1	200	20 mcg CHIKV VLP	20 mcg CHIKV VLP
2	200	PBS	PBS
All injections will be administered IM at 0.5 mL by needle and syringe.			

The Protocol Safety Review Team (PSRT) will review safety data routinely throughout the study. The study will utilize both electronic database features and reviews by designated safety review personnel to identify in a timely manner if any of the safety pause rules of the study are met. The NIAID Intramural DSMB will provide an independent safety review at scheduled intervals to coincide with their biannual meeting schedule.

No formal statistical interim analysis intended to terminate the trial early for futility or efficacy is planned. Therefore, no p-value adjustments will be made.

4.2 Study Design Issues

The design for this study is a simple parallel group double-blind randomized control using PBS as the control. Following screening, eligible subjects are enrolled; enrollment includes subject randomized to a treatment assignment and administration of the first injection based on the randomization assignment. Subjects who are randomized but whom do not receive a study injection (for example a subject who is randomized but then decides not to participate prior to receiving the Day 0 injection) will not contribute to the analysis cohorts.

4.3 Selection of Study Population

The study is designed for the enrollment of healthy adults. The following eligibility criteria will be used.

Inclusion Criteria

A subject must meet all of the following criteria:

1. 18 to 60 years old
2. Available for clinical follow-up through Study Week 72
3. Able to provide proof of identity to the satisfaction of the study clinician completing the enrollment process
4. Able and willing to complete the informed consent process
5. Willing to donate blood for sample storage to be used for future research
6. In good general health, with a BMI ≤ 40 , without clinically significant medical history, and has satisfactorily completed screening
7. Physical examination and laboratory results without clinically significant findings within the 56 days prior to enrollment

Laboratory Criteria within 56 days prior to enrollment:

8. Hemoglobin either within institutional normal limits or accompanied by site physician approval as consistent with healthy adult status
9. White blood cells either within institutional normal range or accompanied by site physician approval as consistent with healthy adult status
10. Platelets = 125,000 – 500,000/mm³
11. Alanine aminotransferase (ALT) ≤ 1.25 x upper limit of normal (ULN)
12. Serum creatinine ≤ 1.1 x ULN based on site institutional normal range
13. Negative result on an HIV test that meets local standards for identification of HIV infection
14. Negative result on the CHIKV screening antibody assay.

Criteria applicable to women of childbearing potential:

15. Negative human chorionic gonadotropin pregnancy test (urine or serum) on day of enrollment
16. Agree to use an effective means of birth control from 21 days prior to enrollment through 12 weeks after the last study injection

Exclusion Criteria

A subject will be excluded if one or more of the following conditions apply:

Women Specific:

1. Planning to become pregnant during the 16 weeks after enrollment in the study

Subject has received any of the following substances:

2. Systemic immunosuppressive medications within 2 weeks prior to enrollment
3. Blood products within 16 weeks prior to enrollment
4. Immunoglobulin within 8 weeks prior to enrollment
5. Prior vaccinations with an investigational CHIKV vaccine
6. Investigational research agents within 4 weeks prior to enrollment
7. Any vaccination within 2 weeks prior to enrollment
8. Current anti-TB prophylaxis or therapy

Subject has a history of any of the following clinically significant conditions:

9. A history of immune-mediated or clinically significant arthritis
10. Serious reactions to vaccines that preclude receipt of study injections as determined by the investigator
11. Hereditary angioedema, acquired angioedema, or idiopathic forms of angioedema
12. Asthma that is unstable or required emergent care, urgent care, hospitalization or intubation during the past two years or that is expected to require the use of oral or intravenous corticosteroids
13. Diabetes mellitus (type I or II), with the exception of gestational diabetes
14. Idiopathic urticaria within the past year
15. Bleeding disorder diagnosed by a doctor (e.g. factor deficiency, coagulopathy, or platelet disorder requiring special precautions) or significant bruising or bleeding difficulties with IM injections or blood draws
16. Malignancy that is active or history of a malignancy that is likely to recur during the period of the study
17. Seizure in the past 3 years or treatment for a seizure disorder within the last 3 years
18. Asplenia, functional asplenia or any condition resulting in the absence or removal of the spleen
19. Psychiatric condition that may preclude compliance with the protocol; past or present psychoses; or a history of suicide plan or attempt within the five years prior to enrollment

20. Any medical or social condition that, in the judgment of the investigator, is a contraindication to protocol participation or impairs a volunteer's ability to give informed consent

4.4 Subject Discontinuations

A subject may be discontinued from receiving study injections for the following reasons:

- Pregnancy;
- Grade 3 AE assessed as related to a study injection (with the exception that self-limited Grade 3 solicited reactogenicity does not require discontinuation of study injections);
- Grade 4 AE assessed as related to a study injection;
- Immediate hypersensitivity reaction associated with a study injection;
- CHIKV infection or other intercurrent illness that is not expected to resolve prior to the scheduled study injection assessed by study clinician to require withdrawal from the injection schedule;
- Treatment with systemic glucocorticoids (e.g., prednisone or other glucocorticoid) or other immunomodulators (other than nonsteroidal anti-inflammatory drugs [NSAIDs]), with the exception that, study injection may continue per investigator discretion if the next one occurs at least 2 weeks following completion of glucocorticoid treatment;
- The study PI assesses that it is not in the best interest of the subject to continue on the injection schedule.

A subject may be discontinued from protocol participation for the following reasons:

- Subject voluntarily withdraws;
- Subject develops a medical condition that is a contraindication to continuing study participation;
- The Investigational New Drug (IND) sponsor or regulatory authorities stop the protocol;
- The study PI assesses that it is not in the best interest of the subject to continue participation in the study or that the subject's compliance with the study is not sufficient.

4.5 Treatments

4.5.1 Treatments Administered

The active vaccine under study is 20 mcg dose of VRC-CHKVLP059-00-VP, an investigational VLP vaccine that consists of the E1, E2 and capsid proteins of CHIKV (strain 37997). The control is VRC-PBSPLA043-00-VP, sterile phosphate-buffered saline (PBS) prepared for human injection. Subjects will receive 2 intramuscular (IM) injections via needle and syringe.

4.5.2 Method of Assigning Subjects to Treatment Groups (Randomization)

For each clinical site, randomization will be 1:1 allocation within each stratum of age group to either the CHIKV VLP vaccine or PBS placebo. The randomization sequence was generated in SAS using permuted blocked randomization with randomly selected block sizes of two or four.

Randomizations will be done online using an electronic randomization system. The randomization code was prepared by the Protocol Statistician and included in the enrollment module for the trial. The randomization code will link to the treatment assignment. To decrease the potential for subject dropouts during the period between randomization and initial injection, the electronic data system will assign each subject a randomization code on Day 0 after confirmation of eligibility to begin Day 0 study injections has been entered into the system. Manual randomization back-up procedures and instructions will be provided for use in the event that the site temporarily loses access to the Internet or the online enrollment system is unavailable to a study site.

If an individual is screened but does not enroll into the clinical trial, screening records will be kept to document the reason the individual did not enroll.

